9.5.9. Chest X-ray

Table 105. Shift-table of chest X-ray results before and after treatment

9.5.10. ECG

Table 106. Shift-table of ECG examination results before and after treatment

9.5.11. Concomitant medication and medication adherence

Table 107. Concomitant medication

Items	Indicator	Experimental group	Control group	Total
Concomitant medication	No n (%)			
	Yes n (%)			
	Total (Missing)			
	Statistics			
	P-value			

Table 108. Medication adherence

Items	Indicator	Experimental group	Control group	Total
Adherence to tacrolimus capsules/mycophenolate mofetil dispersible tablets (%)	N (Missing)			
	Mean (SD)			
	Median			
	Q1, Q3			
	Min, Max			
	Statistics			
	P-value			
Adherence to tacrolimus capsules/mycophenolate mofetil dispersible tablets	Excellent (80-120%) n (%)			
	Poor (<80% or >120%) n (%)			
	Total (Missing)			
	Statistics			
	P-value			
Adherence to steroids (%)	N (Missing)			
	Mean (SD)			
	Median			
	Q1, Q3			
	Min, Max			
	Statistics			
	P-value			
Adherence to steroids	Excellent (80-120%) n (%)			
	Poor (<80% or >120%) n (%)			
	Total (Missing)			
	Statistics			
	P-value			

10. Attachments

Table 109. List of subjects drop-out (All randomized subjects)

Site	Subject code	Random number	Group	Drop-out	Trial completion	Termination date	Treatment discontinuation reason	FAS	PPS	SS	Reason for not be included in the PPS

Table 110. List of subjects exclusions (All randomized subjects)

Site	Subject code	Random number	Group	Exclusion	Trial completion	Termination date	Treatment discontinuation reason	FAS	PPS	SS	Reason for not be included in the PPS

Table 111. List of protocol deviations (All randomized subjects)

Note: Analysis based on external file "XX".

Table 112. List of demographic characteristics (FAS)

Site	Subject code	Random number	Group	Date of birth	Age (years)	Gender	Ethnicity	Other ethnicity	Source of disease	Height (cm)	Weight (kg)	BMI (kg/m ²)

Table 113. List of family history and personal history (FAS)

Site	Subject	Random	Group	Family history	History of drug allergy	History of surgery	History of pet ownership	Number of gestation	Number of parturition	Birth weight (kg)	History of dystocia	Feeding history	Partial eclipse	History of growth and development	Vaccination history
code	code	number													

Table 114. List of history of other diseases and concomitant medications (FAS)

Site	Subject code	Random number	Group	Disease name	Start date	End date	Disease persists or not	Drug name	Drug dosage form	Dosage	Frequency	Still on medication or not

Table 115. List of history of nephrotic syndrome (FAS)

Site	Subject code	Random number	Group	Onset date	Diagnosis date	Course of disease	No. of relapses in the past 1 year	No. of relapses in the past 6 months	Time to recurrence	Negative conversion time of urine protein

Table 116. List of treatment history for nephrotic syndrome (FAS)

Site	Subject code	Random number	Group	Drug name	Drug dosage form	Dosage	Frequency of medication	Start medication date	Stop medication date	Still on medication or not

Table 117. List of disease relapse (urine protein) situations (FAS)

Site	Subject code	Random number	Group	Visit	Relapse or not	Serial number	Relapse start date	Relapse end date	Description of relapse

Table 118. List of primary efficacy indicator (1-year relapse-free) situations (FAS/PPS)

Site	Subject code	Random number	Group	Relapse or not	Relapse start date	Relapse end date	Random date	Analyze date	Endpoint event

Table 119. List of secondary efficacy indicator (first relapse after enrollment) situations (FAS/PPS)

Site	Subject code	Random number	Group	Relapse or not	Relapse start date	Relapse end date	Random date	Analyze date	Endpoint event

Table 120. List of secondary efficacy indicator (6-month relapse-free) situations (FAS/PPS)

Site	Subject code	Random number	Group	Relapse or not	Relapse start date	Relapse end date	Random date	Analyze date	Endpoint event

Table 121. List of blood routine examination results that were normal before treatment and abnormal after treatment (SS)

Site	Subject code	Random number	Group	Examination items	Visit	Baseline result	Baseline unit	Baseline clinical judgment	Visit result	Visit unit	Visit clinical judgment

Table 122. List of urine routine examination results that were normal before treatment and abnormal after treatment (SS)

Site	Subject code	Random number	Group	Examination items	Visit	Baseline result	Baseline unit	Baseline clinical judgment	Visit result	Visit unit	Visit clinical judgment

Table 123. List of serum biochemistry results that were normal before treatment and abnormal after treatment (SS)

Site	Subject code	Random number	Group	Examination items	Visit	Baseline result	Baseline unit	Baseline clinical judgment	Visit result	Visit unit	Visit clinical judgment

Table 124. List of urine test results that were normal before treatment and abnormal after treatment (SS)

Site	Subject code	Random number	Group	Examination items	Visit	Baseline result	Baseline unit	Baseline clinical judgment	Visit result	Visit unit	Visit clinical judgment

Table 125. List of eGFR results that were normal before treatment and abnormal after treatment (SS)

Site	Subject code	Random number	Group	Visit	Baseline result	Baseline clinical judgment	Visit result	Visit clinical judgment

Table 126. List of chest X-ray results that were normal before treatment and abnormal after treatment (SS)

Site	Subject code	Random number	Group	Visit	Baseline result	Baseline clinical judgment	Visit result	Visit clinical judgment	Description of abnormal

Table 127. List of ECG examination results that were normal before treatment and abnormal after treatment (SS)

Site	Subject code	Random number	Group	Visit	Baseline result	Baseline clinical judgment	Visit result	Visit clinical judgment	Description of abnormal

Table 128. List of AE (SS)

Site	Subject code	Random number	Group	AE ID	Description of AE	Severity	Start date	Treatment or not	AE ended or not	End date	Treatment	Relationships	Measures taken on
												with drug	study drug

Table 129. List of AE-continued (SS)

Site	Subject code	Random number	Group	AE ID	Description of AE	AE outcomes	Recovery/cure date	Details of sequelae	Death date	SAE or not	Cause withdraw or not

Table 130. List of SAE (SS)

Site	Subject code	Random number	Group	SAE ID	Type of SAE	Report date	Description	SAE situations	Death date	Severity	Onset Date	SAE	Relationships with
							of SAE					outcomes	drug

Table 131. List of SAE-continued (SS)

Site	Subject code	Random number	Group	SAE ID	Type of SAE	Report time	Description	Measures taken on	Reported SAE situation	Details of SAE occurrence
							of SAE	study drug		and treatment

Table 132. List of concomitant medication (SS)

Site	Subject code	Random number	Group	CM	China approved	Administration	Single dose	Unit	Frequency	Purpose of	Dosing start date	Still in use	Dosing end date
				ID	drug names	route				medication

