4.5.4. Withdrawal criteria

Patients are free to withdraw from the trial at any time without any reason.

Patients must withdraw from this research in the following conditions:

- (1) Withdrawal of the Informed Consent Form.
- (2) Violation of the inclusion criteria or compliance with the exclusion criteria.
- (3) No administration of the test drug according to the Protocol for 14 consecutive days due to various reasons.
- (4) For two consecutive times, the measured value of SCr with an interval of at least 4 weeks has increased more than twice the baseline, and eGFR < 60mL/min.1.73m².
- (5) The target concentration of tacrolimus or mycophenolate mofetil can not be reached after dose adjustment for one month.
- (6) ALT or total bilirubin levels reach more than 2 times of the upper limit after medication, with a continuous increase for 2 weeks; if ALT or total bilirubin levels still rise to more than 2 times of the

upper limit after 2 weeks of liver protection drug treatment, stop the test drug. In case of no recovery after 2 weeks of drug withdrawal, the patient shall withdraw from the test.

(7) Occurrence of unknown adverse events of unacceptable nature, severity and/or duration, or occurrence of known unacceptable adverse events or the occurrence frequency exceeding expectations.

(8) The clinical events or safety-affecting events result in withdrawal from the clinical trial, and the investigators believe that such subjects shall withdraw from the trial.

(9) If pregnancy occurs during treatment, withdraw from the trial.

(10) Unauthorized use of drugs prohibited by this research.

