7.1. Analysis data set

Full analysis set (FAS): It refers to the set of eligible cases and drop-off cases. The cases are required to have evaluation data after at least one treatment, but excluding the eliminated cases. Per-protocol set (PPS): It refers to the set of cases that meet the inclusion criteria, do not meet the exclusion criteria and complete the treatment plan, that is, the analysis of cases that meet the trial protocol, have good compliance and complete the specified content in CRF (PP analysis).

Safety set (SS): It refers to the actual data with safety index records after receipt of at least one treatment. The missed safety values shall not be carried forward. It includes some eliminated cases that can be evaluated, such as those whose age exceeds the inclusion criteria, but excludes those whose safety judgment cannot be made due to the use of banned drugs. For the incidence of adverse reactions, the number of cases in the safety set is used as the denominator.

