8.1.5. Other analysis

- (1) Case distribution: Different data sets in each group, case distribution in each Site, comparison of total drop-off rate, detailed list of termination reasons, and descriptive analysis.
- (2) Compliance analysis: Compare whether the two groups of patients take the test drugs on time and in quantity, whether they take the drugs and foods prohibited in the Protocol, and conduct the same descriptive analysis as well as χ^2 test or Fisher test for analysis.
- (3) The incidence of drug withdrawal or drug change due to adverse reactions in the clinical trial shall be analyzed with χ^2 test or Fisher test. The efficacy in the long-term follow-up after the trial is evaluated by descriptive analysis and χ^2 test or Fisher test.

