9.5. Safety analysis (SS)

9.5.1. Adverse event (AE)

Table 62. Between-group comparison of AE

Items	Experimental group			Control group			P-value
	No. of AEs	No. of subjects	Percentage	No. of AEs	No. of subjects	Percentage	
AE							
AE of severe severity							
Drug-related AE							
Serious adverse event (SAE)							
Drug-related SAE							
Drop-out due to AE							
Drop-out due to SAE							

Note 1: The definitions related to drugs are “definitely related”, “probably related”, “possibly related”, “unlikely related” and “not related”.

Note 2: The data of SAE that cause the drop-out came from the external file “XX”.

Table 63. characteristics of AE in each group

Items	Experimental group			Control group			P-value
	No. of AEs	No. of subjects	Incidence	No. of AEs	No. of subjects	Incidence	
Relationship with study drug							
Definitely related							
Probably related							

Items	Experimental group			Control group			P-value
	No. of AEs	No. of subjects	Incidence	No. of AEs	No. of subjects	Incidence	
Possibly related							
Unlikely related							
Not related							
Outcome	Recovered/resolved						
	Recovered/resolved with sequelae						
	Not recovered						
	Recovering/resolving						
	Death						
	Unknown						

Table 64. Between-group comparison of SAE

Items	Experimental group (n=XX)			Control group (n=XX)			Total (n=XX)	P-value
	No. of AEs	No. of subjects	Incidence (%)	No. of AEs	No. of subjects	Incidence (%)		
Results in death								
Requires hospitalization								
Prolongs hospitalization								
Disability								
Dysfunction								
Congenital malformation								
Life threatening								
Other								

Table 65. Summary of AE base on SOC and PT coding

Indicator	Experimental group (n=XX)			Control group (n=XX)			Total (n=XX)	P-value
	No. of AEs	No. of subjects	Incidence (%)	No. of AEs	No. of subjects	Incidence (%)		
AE								

Indicator	Experimental group (n=XX)			Control group (n=XX)			Total (n=XX)			P-value
	No. of AEs	No. of subjects	Incidence (%)	No. of AEs	No. of subjects	Incidence (%)	No. of AEs	No. of subjects	Incidence (%)	
SOC1										
PT1										
PT2										
...										
SOC2										
PT1										
PT2										
...										

Table 66. Summary of adverse reactions base on SOC and PT coding

Indicator	Experimental group (n=XX)			Control group (n=XX)			Total (n=XX)			P-value
	No. of AEs	No. of subjects	Incidence (%)	No. of AEs	No. of subjects	Incidence (%)	No. of AEs	No. of subjects	Incidence (%)	
Adverse event										

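### The planned arm comparison of prohibited-drug use has no stated population and no table shell, and the only on-study concomitant-drug outputs use a safety set that can leave out banned-drug users

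*SAP*

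**What the plan says.** - **Planned comparison.** SAP 8.1.5(2) compares the arms on taking the test drugs on time and in quantity, and on "whether they take the drugs and foods prohibited in the Protocol". The method is to "conduct the same descriptive analysis as well as" a chi-square or Fisher test. No analysis set is named.
- **Same comparison in the protocol.** It appears in Protocol 11.3.5, under a heading for other efficacy analysis. Protocol 11.3.2 adopts the FAS for all effectiveness analyses.
- **Safety set.** SAP 7.1, like Protocol 11.1, takes children with safety records after at least one treatment, but "excludes those whose safety judgment cannot be made due to the use of banned drugs".
- **Outputs.** Tables 107 and 108 form SAP section "9.5.11. Concomitant medication and medication adherence", under the heading "9.5. Safety analysis (SS"). Table 107 has one item: any concomitant medication, yes or no. Table 108 gives adherence to the test drug and to steroids. The listing in SAP section 10 carries its own label: "Table 132. List of concomitant medication (SS"). Tables 109 to 111 (drop-outs, exclusions, protocol deviations) cover all randomised children.
- **Banned drugs.** SAP 5.3 prohibits other immunosuppressants, biological agents, plasma exchange and Chinese herbal medicines for kidney disease. Among the withdrawal criteria in SAP 4.5.4 is "Unauthorized use of drugs prohibited by this research".

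**The concern.** An output meant to show who took which drugs should not be restricted by a rule that removes children because of the drugs they took. Every child removed by that clause is a banned-drug user, so the clause can only lower the prohibited use seen in Tables 107 and 132.

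Prohibited immunosuppressants and biological agents could plausibly affect relapse, the primary outcome. The trial is open-label, so their use may differ by arm. A reader who wants to know how far such use bears on the relapse comparison needs it counted by arm in an unselected population. As written, the plan promises the comparison but does not say in whom it is made or where it is reported.

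**Working it through.** The documents give no figure for banned-drug use or for exclusions from the safety set, so there is no stated number to reproduce. The check has two parts.

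**1. Is there an output for the comparison, and on which set?**

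| Output | Content | Population |
|---|---|---|
| SAP 8.1.5(2), text | Arm test of prohibited-drug use | Not stated |
| Table 107 | Any concomitant drug, yes/no, with P-value | Safety set, by its place in 9.5 |
| Table 132 | Listing of each concomitant drug, no test | Safety set, by its label |
| Table 111 | Listing of deviations from an external file, no test | All randomised |
| Table 3 | Discontinuation reasons; no prohibited-drug category | All enrolled |

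No shell counts prohibited drugs. The only shells that handle on-study concomitant drugs use the safety set.

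**2. What can the safety-set clause do to a count?**

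Let *n* be the children in an arm, *u* the banned-drug users among them, and *x* the users removed because safety cannot be judged (0 ≤ *x* ≤ *u*). Each removed child leaves both numerator and denominator:

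observed rate = (*u* − *x*)/(*n* − *x*)

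This never exceeds *u*/*n*, because *n*(*u* − *x*) ≤ *u*(*n* − *x*) reduces to *u* ≤ *n*. It is lower whenever *x* > 0 and *u* < *n*.

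Take *n* = 135 per arm (SAP 4.2.2). The values of *u* and *x* are assumptions for illustration, and A and B are arbitrary arms.

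| Users A v B | Removed A v B | All 135 per arm | Safety set |
|---|---|---|---|
| 8 v 8 | 0 v 0 | 5.9% v 5.9% | 8/135 v 8/135 = 5.9% v 5.9% |
| 8 v 8 | 4 v 4 | 5.9% v 5.9% | 4/131 v 4/131 = 3.1% v 3.1% |
| 8 v 8 | 8 v 8 | 5.9% v 5.9% | 0/127 v 0/127 = 0% v 0% |
| 5 v 12 | 2 v 8 | 3.7% v 8.9% | 3/133 v 4/127 = 2.3% v 3.1% |
| 5 v 12 | 0 v 12 | 3.7% v 8.9% | 5/135 v 0/123 = 3.7% v 0% |
| 5 v 15 | 0 v 10 | 3.7% v 11.1% (P = 0.034) | 5/135 v 5/125 = 3.7% v 4.0% (P = 1.00) |
| 20 v 7 | 10 v 4 | 14.8% v 5.2% (P = 0.014) | 10/125 v 3/131 = 8.0% v 2.3% |

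P-values are from two-sided Fisher tests. The effect runs from none (first row) to complete disappearance of the users (third row). Unequal removal can hide an arm difference (sixth row) or reverse it (fifth row).

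**The case against.** The strongest reply is that the plan never assigns the prohibited-drug comparison to the safety set. SAP 8.1.5 stands apart from 8.1.6, where the safety set is invoked, and the protocol puts the same comparison under an efficacy heading governed by the FAS. This stands. A reader might infer from the table labels that the planned test is undercounted by rule. The documents do not support that, because the set for the test is simply not stated. The protocol's pointer does not settle it either, since the SAP retitles the section as other analysis, without the word efficacy.

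Second, the clause removes only users whose safety cannot be judged, not all banned-drug users. This also stands: the loss may be zero and cannot be sized from the documents.

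Third, a reader might infer that the removed children remain in the primary analysis while missing from the drug tables. There is text for this: the FAS is defined with "It refers to the set of eligible cases and drop-off cases", and banned-drug use is a withdrawal criterion, not a listed elimination criterion. But the safety-set clause can be read as referring to eliminated cases, which the FAS excludes. Elimination in SAP 4.5.3 also covers failure to complete follow-up as planned, while the note to Table 1 defines elimination differently. The point is unresolved and should not be asserted.

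Fourth, the children can be partly traced. Tables 109 and 110 carry group and analysis-set flags, Table 111 lists deviations, and Table 3 gives set counts by arm. This limits the harm, but none of these tables compares prohibited use between arms.

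Last, the clause does not select on adherence, so any effect on Table 108 is indirect.

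**Conclusion.** The point holds in this form: a planned between-arm comparison has no stated population and no shell, and the only on-study concomitant-drug outputs use a set defined partly by the behaviour of interest. Understatement in Tables 107 and 132 is possible, not certain. It ranges from zero to all users and may differ by arm. Every rate used to illustrate it is assumed.

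The safety-set status of Table 107 rests on its place under the 9.5 heading; that of Table 132 rests on its own label. The primary log-rank and Cox analyses are not altered. What is affected is the reader's ability to judge whether prohibited treatment bears on the relapse result. The correction is worth making because it is specific and nearly free.

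**What to change.** 1. In SAP 8.1.5(2), state the population for the prohibited-drug comparison: all randomised children, as already used for Tables 109 to 111, or all who received at least one dose. Use the same population for Tables 107 and 132.
2. Add to Table 107 a row for any prohibited drug or treatment (as listed in SAP 5.3), by arm, with the planned chi-square or Fisher test. Derive it per child from the concomitant-medication records before any child is removed from an analysis set. Relabelling alone would not be enough, because Table 107 now counts any concomitant drug.
3. For Table 108, use all children who received at least one dose, since adherence has no meaning in a child who was never dosed.

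The cost is one extra table row, changed population labels and a sentence in SAP 8.1.5(2). No new data are needed: the flow chart already records concomitant medication at every visit.
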